The impact estimate is the regression-adjusted difference between the average outcomes of treatment group participants and control group participants. Impact estimates with p-values less than 0.05 (two-tailed test) will be considered statistically significant and provide evidence that there are likely true differences between the groups as a result of NFP.

In addition to these impact estimates, we will also report the percentage of treatment group participants who reported living in a low-income zip code (LIZC) at the time of study enrollment. (LIZC is defined as a zip code in which fifteen percent (15%) or more of households have incomes below the federal poverty guidelines according to 2012 Census Bureau Data.) Before reporting this percentage, we will use Google Map’s Application Programming Interface (API) to confirm that the participant’s self-reported zip code corresponds with their self-reported street address. To do this, we will send a file of unformatted, raw street addresses, cities, and states to Google’s API to return formatted addresses, including zip code. We will then compare these formatted zip codes to the zip codes reported by each study participant. The file we send to Google Map’s API will include a greater number of ‘fake’ (i.e. non-study participant) addresses than actual addresses, to maintain study participants’ confidentiality.

We will also analyze how the main impact estimates vary within our sample. In particular some mothers and their children may be at higher risk for adverse outcomes such as preterm birth or childhood injury. We will define “risk” based on poverty rate in the census tract in which a mother is enrolled. In order to perform this analysis, we will match participants’ self-reported addresses to census tracts in two ways. First, we will send a de-identified file that will only include a randomly generated ID number and the following address information of unformatted, raw street addresses, cities, states, and zip codes to the United States Census Bureau’s Geocoder tool as well as to the geocoding service, Geocodio. We will match addresses to census tracts using both the Census Bureau Geocoder tool as well as Geocodio in order to be able to cross validate the accuracy of the census tract mapping. Mapping to the wrong census tract or failing to map to a census tract will reduce the accuracy of our analysis. The randomly generated ID number will allow for linking census tract

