5.2. Is there a sample size/power calculation?

Yes: If yes; describe the calculation and the scientific rationale, and, if applicable, by site and key characteristics such as participant demographics

NFP plans to serve 4,000 families in South Carolina between January 2016 and January 2020. Our power analysis suggests that with 4,000 families served in the treatment group, we will need a 2:1 T:C ratio (or 2,000 control group families) to achieve 80% or higher chance of detecting statistically significant effects on two out of the three primary outcomes (pre-term birth, birth spacing, and childhood injury), if the true effect size of the outcomes equals the expected effect size provided by NFP. These expected effect sizes are based on analysis of previous NFP trials and baseline knowledge on the current population of South Carolina's Medicaid-eligible first-time mothers and the assumptions summarized below.

As of May, 2015, the expected effective sizes, in percentage difference between the treatment group and the control groups, is -20% for the measure of pre-term birth, -18% for the measure of birth spacing, and -13% for the measure of child injury. In addition, we need 95% or more of women randomized into the treatment group to receive NFP services, and at most 5% of the control group that receives a home visiting program that has as much impact as NFP. Furthermore, our power calculation is based on the assumption that the distribution of the outcomes variables have the following mean (standard deviation) combinations in the absence of NFP intervention: 0.12 (0.32) for the binary measure for pre-term birth, 0.14 (0.34) for the binary measure of birth spacing, and 0.18 (0.30) for the measure of child injury.

With this set of assumptions, we need to enroll at least 6,000 women into the evaluation with a 2:1 treatment to control ratio to achieve near 80% or higher power. With these numbers we will have roughly 70% power to detect a statistically significant effect on the birth-spacing measure if the true effect size is -18%. We will have a nearly 100% chance to detect a statistical significant effect on the child injury measure if the true effect size is -13%. We will not have sufficient statistical power to detect the expected effect (-20%) on the pre-term birth measure; the minimum detectable effect size with 80% power for the pre-term birth measure is -30%.

6. Recruitment Methods

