- Who will be able to see the PHI for research purposes
- What types of PHI will be collected
- Where the PHI will be collected from
- How the PHI will be protected to maintain each participant's privacy and confidentiality
- How the PHI will be used

The consent form and the NFP staff who will be conducting the informed consent process will make it clear to the participant that by signing the consent form, she is authorizing the study team to use her and her children's PHI. The participant will also be informed that she may cancel this authorization at any time by contacting the study team, in writing, at the address on the consent form. If she decides not to authorize the investigators to use her PHI or she cancels this authorization, she and her children will no longer be able to participate in this research study, and the use or sharing of future PHI will be stopped. However, the PHI that has already been collected may still be used.

14. Data and Specimen Banking

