## **A.2. Characterizing missing data**

We may be unable to track mother and child outcomes for pregnant women enrolled in our trial over the entire period spanning pregnancy and the child's first two years of life for various reasons. First, we may be unable to match the identifying information provided by women at study enrollment to administrative records because of poor data quality or because women enrolled in the trial moved out of state. Second, we may be unable to match women to their index birth because of problems linking mother and child records within South Carolina's administrative record system or because their pregnancy ended in pregnancy loss. We may be unable to observe child outcomes through 24 months if a child dies before reaching 24 months of age. For outcomes that can only be observed in Medicaid claims data, such as child preventative health outcomes and outpatient care utilization for mothers, we will not observe outcomes for mothers or children not enrolled in Medicaid. Whenever possible, we will report missing outcome data and characterize missing outcome data across each of these groups. More details are provided in Addendums 1-3 regarding plans to characterize missing outcome data related to each of the three domains of potential program impact and plans for sensitivity analyses to account for potential patterns in missing outcome data.

Because administrative records update continuously over time, we anticipate that mothers and babies classified as falling within our study sample definitions may change as administrative data is updated. For example, a mother enrolled in the trial whom we cannot initially match to any records may later match to state Medicaid records. Furthermore, administrative data may experience delayed reporting or data errors that are corrected later. We may revisit analyses several years after completion to assess the robustness of results to updated administrative records.

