#### **2.1. Defining the Sample for Analysis**

Our sample for analysis of our primary child-health related outcome will be restricted to mother-baby dyads with an identified index birth as defined in section A.1 of the pre-analysis plan. All analysis will take place at the mother level, where randomization occurs. We discuss how outcomes will be operationalized in the case of multiple births below. We will not restrict the sample based on matching to Medicaid data as the outcomes include utilization that will be observable in all-payer hospital discharge data. For outcomes that rely primarily on Medicaid data (i.e. outcomes related to preventive child health utilization), we may restrict the sample to mother-baby dyads where children retain either partial or continuous Medicaid coverage through the child's first or second year of life. We anticipate that the children of most mothers who enroll in the trial will be eligible for Medicaid for their entire first year of life but we anticipate that more children may drop off of Medicaid during their second year of life, whether because of the need to document eligibility or because of changes in eligibility in the second year of life during some periods of the study (see Table 2). We discuss the potential differences in Medicaid enrollment between control and treatment arms and planned sensitivity analyses and alternative specifications in section 2.4.

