### 3.3. Timing of Study analyses

We will complete this analysis once all study births have occurred, and at least 24 months have elapsed following the last study birth. We will add additional lags to account for the time it takes for administrative records to be complete, sent to the study team, and matched to existing analytic files. Based on the estimated delivery date collected in the baseline survey, the latest expected study delivery date is November 7, 2020. As we define births within a 120-day window of the estimated gestational age as a study index birth, the latest possible date when a study index birth could occur is March 7, 2020. We will allow for twenty-four months of follow-

up from the time of the final possible study index birth (March 7, 2022), six additional months for the study outcomes to be fully incorporated into South Carolina administrative data (September 7, 2023), and an additional three-month buffer for the administrative data to be matched with the study dataset (December 7, 2023). Therefore, we anticipate that analyses of these outcomes will begin in December 2023.

This study includes four birth spacing outcomes. The first three are birth interval indicators defined as having no subsequent live birth observed within 21 (primary outcome), 15 and 24 months (secondary outcomes) of the index birth. The fourth is a continuous outcome defined as the number of months before any subsequent birth within 60 months of the index birth. The analysis for this outcome will include only women who went on to have another birth within 60 months of their index birth. The first three of the birth spacing outcomes described in Table 3.1 will be reported in the main manuscript for the maternal life course objective. The continuous birth interval outcome will be included in a later manuscript which will include longer-term maternal outcomes.

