### **3.4. Attrition and Missing Outcome Data**

As described in section 1.4 some mother-babies will be matched to a childbirth-related Medicaid claim or discharge record but unmatched to a birth certificate record or fetal death vital record. We will conduct a sensitivity analysis that will include these study participants, in addition to the main sample following procedures defined in section 1.6.1. For mother-babies without a birth certificate or fetal death record, we will use hospital discharge data as the date of birth or fetal death.

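### Families who leave South Carolina after the index birth are scored event-free on birth spacing and child injury, and no sensitivity analysis addresses this

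*SAP*

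**What the plan says.** **Birth spacing.** SAP 3.1 admits every woman with an index birth or fetal death. SAP 3.2.1 takes the data from vital statistics birth records. SAP 3.3 defines the indicators as "having no subsequent live birth observed within 21 (primary outcome), 15 and 24 months (secondary outcomes) of the index birth".

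**Child injury, abuse or neglect.** SAP 2.1 admits every dyad with an index birth and adds: "We will not restrict the sample based on matching to Medicaid data as the outcomes include utilization that will be observable in all-payer hospital discharge". Under SAP 2.2 the outcome occurs if a coded encounter or death appears in South Carolina discharge records, Medicaid claims or mortality records.

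**Missing data.** SAP A.2 says outcomes may not be trackable across pregnancy and the child's first two years. Among its reasons for failing to match women to records is "because women enrolled in the trial moved out of state". It refers the reader to Addendums 1-3 for sensitivity analyses. In those addenda:

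- SAP 3.4 addresses the case where "some mother-babies will be matched to a childbirth-related Medicaid claim or discharge record but unmatched to a birth certificate record or fetal death vital record", which is a missing link at the index birth.
- SAP 3.5 compares Medicaid coverage by arm, for the contraception outcomes.
- SAP 2.4 reports by arm child deaths and children never matched to Medicaid eligibility.
- SAP 2.5 compares child Medicaid enrolment by arm and repeats the primary outcome without Medicaid data.

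**Cancelled authorization.** Protocol 13.1 (HIPAA) says the woman and her children leave the study and "the use or sharing of future PHI will be stopped. However, the PHI that has already been collected may still be used". The SAP does not mention these women.

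**The concern.** Entry to both samples depends on a record at the index birth. After that, the outcome is whether a further record turns up. Consider a family that moves to another state when the child is six months old. A second birth at 18 months, or an injury treated in the new state, falls outside South Carolina birth and discharge records. No rule removes the family, censors it or marks the outcome missing, so lost observation is counted as a good result.

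If such loss is equal in the arms, the absolute effect shrinks a little. If NFP changes who stays in the state, the comparison is biased, and the bias can run either way. Unequal loss is plausible, because only the treatment arm is offered nurse contact until the child is two, but the documents contain no evidence that it occurs.

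The SAP accepts the principle elsewhere. It expects that NFP may affect who keeps Medicaid, and for antenatal tests in short pregnancies it plans bounds that assume all or none would have been tested. Two primary outcomes have no equivalent protection against loss after the birth.

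**Working it through.** **Inputs**

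- Test (Protocol 5.1): "Impact estimates with p-values less than 0.05 (two-tailed test) will be considered statistically significant".
- Size (Protocol 5.2): "we need to enroll at least 6,000 women into the evaluation with a 2:1 treatment to control ratio", that is 4,000 and 2,000.
- Control means and SDs (Protocol 5.2): "0.14 (0.34) for the binary measure of birth spacing, and 0.18 (0.30) for the measure of child injury".
- Expected relative effects (Protocol 5.2): -18% for birth spacing, -13% for injury.
- Uptake 95%, control exposure 5% (Protocol 5.2): contrast 0.95 - 0.05 = 0.90.
- Loss rates: none in the documents, so assumed.

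**Step 1: reproduce the plan's birth-spacing power**

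- Treatment rate: 0.14 x (1 - 0.18 x 0.90) = 0.11732. Difference: -0.02268.
- Pooled rate: (2,000 x 0.14 + 4,000 x 0.11732) / 6,000 = 0.12488.
- Null SE: sqrt(0.12488 x 0.87512 x (1/2,000 + 1/4,000)) = 0.00905.
- Alternative SE: sqrt(0.11732 x 0.88268/4,000 + 0.14 x 0.86/2,000) = 0.00928.
- Power: Phi((0.02268 - 1.96 x 0.00905) / 0.00928) = 0.703.
- With the unpooled SE throughout: Phi(0.02268/0.00928 - 1.96) = 0.686.

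The plan states roughly 70%, so its figure is reproduced. Its near-100% power for injury is not (54% with proportions, 73% with the stated SD of 0.30, both at contrast 0.90). Nothing below uses that claim. For injury only the 0.18 rate is used.

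**Step 2: model the loss**

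Let a share m of an arm be unobservable for the whole window and scored event-free. The observed rate is p x (1 - m).

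**Step 3: birth spacing with the planned effect**

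| Loss, treatment / control | Observed rates | Difference | Power (unpooled, pooled) |
|---|---|---|---|
| 0 / 0 | 0.1173, 0.1400 | -0.0227 | 0.69, 0.70 |
| 10% / 10% | 0.1056, 0.1260 | -0.0204 | 0.63, 0.65 |
| 5% / 10% | 0.1115, 0.1260 | -0.0145 | 0.37, 0.38 |
| 10% / 5% | 0.1056, 0.1330 | -0.0274 | 0.86, 0.87 |

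Excluding a random 10% of each arm (3,600 and 1,800 left, rates unchanged) gives 0.64 and 0.66. With equal loss, scoring zero costs less than one power point relative to exclusion, and the relative effect is unchanged.

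**Step 4: no true effect**

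The false difference is p x [(1 - m in treatment) - (1 - m in control)]. For 10% / 5% in birth spacing this is 0.14 x (0.90 - 0.95) = -0.007.

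| Loss, treatment / control | Birth spacing: difference, P(reject) | Injury: difference, P(reject) |
|---|---|---|
| 10% / 8% | -0.0028, 0.061 | -0.0036, 0.065 |
| 10% / 5% | -0.0070, 0.118 | -0.0090, 0.142 |
| 15% / 5% | -0.0140, 0.333 | -0.0180, 0.425 |

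With the 3,295 and 1,637 index births in SAP Addendum 4, Table 3, the 10% / 5% row becomes 0.106 and 0.125.

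**Step 5: do the planned checks reach this?**

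The analysis without Medicaid data in SAP 2.5 still relies on South Carolina discharge and mortality records, so a mover stays event-free in it. SAP 3.4 repairs index-birth links only. The Medicaid comparisons in 2.4, 2.5 and 3.5 describe coverage by arm and leave the scoring unchanged.

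**The case against.** **The Medicaid comparisons could reveal unequal loss.** SAP 2.4 reports by arm the children with no Medicaid match in months 13-24. SAP 2.5 and 3.5 compare enrolment by arm and test baseline balance among those enrolled. This stands in part: a reader might infer that unequal loss would go wholly unseen, and that is too strong. But coverage is a weak proxy for residence. SAP Table 2 puts the parental limit at 67% of poverty in January 2016 to 2020, against 199% in pregnancy, so many mothers who stay will lose coverage. A signal there would also lead to no re-analysis of birth spacing.

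**The A.2 phrase on moving concerns enrolment identifiers that fail to match, which SAP 1.4 reports by arm.** That is the immediate context. The opening sentence of A.2, however, covers the whole period to the child's second birthday, and 1.4 stops at the pregnancy outcome.

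**Cancelled authorization.** A reader might infer that a woman who cancels is kept and scored event-free. The documents do not say so. Protocol 13.1 says she no longer participates and permits use of data already collected. It does not say that she is analysed or how. Her handling is unspecified, and no count is given.

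**The power loss is small.** For equal loss this is right. Holding the SD at 0.34 while event rates fall would give about 59% power at 10% loss and overstate the cost, because a binary outcome's SD falls with its rate.

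**The rule may be in the published protocol paper** to which the SAP defers for its empirical approach. That paper is not among the documents, so this cannot be excluded.

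**Conclusion.** The point holds for families who leave South Carolina after the index birth. The scoring is not stated in one sentence. It follows from entry fixed at the birth, outcomes that need a later record, and the absence of any censoring or missing-data rule. It is most explicit for birth spacing, where the definition rests on births observed.

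The size depends on loss rates that the documents do not give and on all events being missed among those lost. Loss late in the window matters less. Under those assumptions equal loss is a minor matter, a two-point gap barely moves the error rate, and a five-point gap raises it from 5% to about 12% (birth spacing) and 14% (injury) or roughly halves birth-spacing power, depending on direction. The documents do not show that such a gap exists. The finding is that the plan has no analysis to show how far these two results depend on it. This is an inexpensive improvement and does not call for replacing the primary analysis.

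**What to change.** Keep the primary analysis and add the following.

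1. In SAP 2.4 and 3.4, report by arm the share of dyads with any South Carolina record for mother or child at or after the end of the outcome window. Use sources already linked or under agreement: child Medicaid eligibility, discharge, vital records, SNAP/TANF. Report by arm the number who cancelled authorization.
2. For both primary outcomes, add one sensitivity analysis that varies the assumed event rate among those with no later trace, separately by arm: a tipping point, with worst-case bounds.
3. State that NFP may itself affect the trace (Medicaid retention and SNAP/TANF receipt could both respond to it), so it is not used to exclude women.
4. State that follow-up after a cancellation date is missing, not zero.

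If the published protocol paper already contains such a rule, cite it instead.

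The cost is some SAP wording and a little more analysis, with no new data collection. Some families still in the state will leave no trace and be treated as possibly lost. The worst-case bounds may be wide: with 10% untraced in each arm they lie 0.10 + 0.10 = 20 points apart, against a planned difference of 2.3 points for birth spacing. The tipping point will then be the more informative result.

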#### Antenatal health

- Smoking cessation during pregnancy [vital records data]
  - We will consider an enrollee to have ceased smoking during pregnancy if their vital record indicates that they smoked pre-pregnancy and that they did not smoke during pregnancy.
- Recommended gestational weight gain [vital records data]
  - Gestational weight gain will be classified as “recommended” if it is within the guidelines published by the National Academy of Medicine (formerly the Institute of Medicine).

The guideline-recommended antenatal care services should be received at the appropriate gestational age during the pregnancy. The gestational age at the time of the test will be calculated as the date of the test minus the approximate date of last menstrual period (in days). We will approximate the enrollee's date of last menstrual period using the child's date of birth and obstetrician's estimate of gestational age at delivery from the vital records. If these fields are missing, we will define the approximate date of last menstrual period as the beginning date of the index pregnancy (defined above).

Each of these outcomes can only be measured among pregnancies that reach the gestational age at which the care is recommended. The main analyses will only include pregnancies that last at least as long as the gestational age recommended for each outcome. However, it is possible that NFP has a direct effect on gestational age, which would mean that the sample of mothers observed could differ across treatment and control arms. If that is the case (i.e., if gestational age at birth between treatment and control group is statistically significantly different), then we will conduct a bounding exercise as a robustness check for the guideline-concordant care outcomes. Using Group B Strep as an example, the main analysis will compute the average treatment effect (ATE) among people whose pregnancies last at least 35 weeks. If gestational age is statistically significantly different between control and treatment arms, we will estimate two bounds on this ATE: (1) a recalculated ATE assuming *all* people who

did not reach 35 weeks' gestation would have received the test, and (2) a recalculated ATE assuming *none* of the people who did not reach 35 weeks' gestation would have received the test.

Table 1.3. Codes for analyses of antenatal care utilization and quality

	CPT/HCPCS	NDC	ICD-10

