#### **3.1. Defining the Sample for Analysis**

The sample will be restricted to women with a fetal death or index birth as defined in section A1 of the pre-analysis plan.

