##### **3.2.1. Construction of birth spacing outcomes**

Data will be obtained from vital statistics birth records. In the case of multiples, birth spacing will be measured as the time between the date of birth of the last child from the index pregnancy to the date of birth of the first child from the subsequent pregnancy. There may be cases where the subsequent birth is implausibly close to the index birth. Births that occur less than or equal to 90 days from the index birth will be assumed to be multiple gestation based on guidelines provided by the National Center for Health Statistics. Subsequent births that occur between 90 days and 21 weeks (147 days) after the index birth will be considered outliers and will be dropped from the analysis. We define birth outcomes of interest in Table 3.1.

Table 3.1. Birth spacing outcomes

Birth spacing outcomes	Follow-up
Inter-birth interval of < 21 months (primary outcome)	21 months
Inter-birth interval of < 24 months	24 months
Inter-birth interval of < 15 months	15 months

Inter-birth interval (continuous)	60 months
-----------------------------------	-----------

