**Table 3. Prevalence of vulnerabilities in sample of mothers with an index birth**

	Nurse Home Visiting Group	Usual Care Group
Living in high poverty area	1029/3292 (31.3%)	509/1636 (31.1%)
Recent arrest	152/3269 (4.6%)	73/1626 (4.5%)
High stress	478/3250 (14.7%)	235/1615 (14.6%)
Depression	630/3270 (19.3%)	305/1631 (18.7%)
Housing insecurity	567/3295 (17.2%)	298/1637 (18.2%)
Have not completed high school	742/3295 (22.5%)	354/1637 (21.6%)
Substance use	823/3295 (25%)	441/1637 (26.9%)
Low social support	364/3295 (11%)	181/1637 (11.1%)
Under 18	225/3295 (6.8%)	117/1637 (7.1%)
Not fluent in English	100/3295 (3%)	50/1637 (3.1%)
Food insecurity	811/3286 (24.7%)	375/1630 (23%)
Limited access to healthcare	598/3279 (18.2%)	285/1625 (17.5%)
Do not have a driver's license	940/3252 (28.9%)	467/1611 (29%)
Low financial independence	961/3295 (29.2%)	477/1637 (29.1%)
Fair/poor health	419/3295 (12.7%)	180/1637 (11%)
Limited relationship with child's father	662/3281 (20.2%)	320/1630 (19.6%)
3+ vulnerabilities	1746/3295 (53%)	836/1637 (51.1%)
5+ vulnerabilities	752/3295 (22.8%)	390/1637 (23.8%)
10+ vulnerabilities	23/3295 (0.7%)	15/1637 (0.9%)
Number of vulnerabilities	Nurse Home Visiting Group	Usual Care Group
Mean (SD)	3.02 (2.19)	2.99 (2.23)
Median (IQR)	3 (1, 4)	3 (1, 4)

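### The continuous birth-spacing outcome is analysed only in women who have another birth within 60 months, so births averted by NFP can leave no trace in the estimate

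*SAP*

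**What the plan says.** SAP Addendum 3 lists four birth-spacing outcomes in Table 3.1: indicators at 21 months (primary), 24 months and 15 months, and a continuous interval with 60 months of follow-up. The sample for the addendum is set in 3.1: "The sample will be restricted to women with a fetal death or index birth". Section 3.3 then narrows it for the continuous interval alone: "The analysis for this outcome will include only women who went on to have another birth within 60 months of their index birth". The three indicators go into the main manuscript and the continuous interval into a later one.

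Section 3.5 deals with selection, but only through Medicaid coverage and the contraception outcomes. SAP B.3 makes intention-to-treat the primary specification.

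The SAP does recognise this type of selection elsewhere. In Addendum 1 (Antenatal health), some tests can be measured only in pregnancies that reach a given gestational age. If NFP affects gestational age, it says this is something "which would mean that the sample of mothers observed could differ across treatment and control arms". If gestational age then differs significantly between arms, "we will conduct a bounding exercise as a robustness check for the guideline-concordant care outcomes".

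**The concern.** Whether a woman has another birth by month 60 is settled after randomisation, and changing the timing of later pregnancies is one of the aims of NFP. Keeping only women with a further birth therefore selects on the outcome itself. A woman whose next birth was averted, or moved past month 60, drops out of her arm.

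The estimate then answers a different question: among women who did have another birth, was the gap longer? Read alone, a zero difference could mean no effect or a real fall in repeat births spread evenly over time. If NFP cut later births proportionally more than early ones, the remaining NFP births would be early ones and NFP would appear to shorten spacing.

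This is also the only listed birth-spacing outcome that looks beyond 24 months. A reduction confined to months 24 to 60 appears in no other listed birth-spacing outcome, and here the women concerned are discarded.

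**Working it through.** **The plan's nearest figure.** The documents give no effect size, standard deviation or power for the continuous interval. Protocol 5.2 gives roughly 70% power for the binary spacing measure. Its inputs are "0.14 (0.34) for the binary measure of birth spacing", an 18% reduction, 4,000 against 2,000 women, 95% uptake, and 5% of controls receiving an equally effective service. The diluted difference is 0.14 × 0.18 × (0.95 − 0.05) = 0.0227. The standard error is 0.34 × √(1/2000 + 1/4000) = 0.0093. So z = 2.44 and power is 68% (70% with the two-proportion formula). The figure reproduces.

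**Inputs for the continuous outcome.**
- Women: 3,295 NFP and 1,637 control, from SAP Addendum 4, Table 3 ("Prevalence of vulnerabilities in sample of mothers with an index birth").
- Controls with a birth by 21 months: 14%, taking the binary measure in Protocol 5.2 to be the 21-month one.
- Controls with a birth by 60 months: 47%, an assumption, with 40% to 60% shown as the range.
- Control hazard: zero to month 9; −ln(0.86)/12 = 0.0126 per month over months 9–21; −ln(0.53/0.86)/39 = 0.0124 over months 21–60.

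**Two summaries.** With birth density f and F = the share with a birth by month 60:
- planned mean = ∫ t·f(t) dt / F, over 0 to 60;
- restricted mean in all women = ∫ t·f(t) dt + 60 × (1 − F).

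Controls have a planned mean of 31.76 months (SD 14.6) and a restricted mean of 46.73 months (SD 17.3). The planned analysis leaves out 53% of controls (60% to 40% over the range).

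**Even reduction, by hand.** If every f(t) is multiplied by 0.82, numerator and denominator of the planned mean both shrink by 0.82, so the difference is exactly zero whatever F is. The restricted mean rises by 0.18 × 0.47 × (60 − 31.76) = 2.39 months; with standard error 0.514, z = 4.64. The NFP share with a birth is 0.82 × 47% = 38.5%. About 0.085 × 3,295 = 279 women leave the NFP side of the planned comparison unnoticed.

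**All scenarios** (NFP minus control, months; 47% case, with the results at 40% and 60% in brackets; two-sided 5%):

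| NFP effect | Planned difference | Restricted mean, all women |
|---|---|---|
| 1. 18% of births averted at every interval | 0.0 | +2.4 (2.1, 3.0), z 4.6 |
| 2. Hazard ratio 0.82 | +0.5 (0.4, 0.7), z 0.7 | +2.0 (1.8, 2.3), z 3.9 |
| 3a. 18% averted before month 21, 25% after | −0.46 (−0.50, −0.38); 10% chance of a significantly shorter interval | +2.9 (2.5, 3.7) |
| 3b. As 3a, but 30% after | −0.82 (−0.90, −0.68); 22% chance | +3.2 (2.75, 4.17) |
| 4. 18% averted before month 21 only | +1.0 (1.1, 0.8), power 32% | +1.1, power 60% |
| 5. 18% of births before month 21 postponed evenly to months 21–60 | +1.4 (1.6, 1.1), power 57% (62%, 51%) | +0.65, power 24% |
| 6. 18% averted in months 21–60 only | −1.0 (−1.1, −0.9); 35% chance of a significantly shorter interval | +1.25 (0.97, 1.82), power 67% |

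At 47%, the standard error of the planned difference is 0.64 to 0.68 months.

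**Can the 24-month indicator stand in?** The control share by month 24 is 1 − 0.86 × exp(−0.0124 × 3) = 17.1%.
- Scenario 1: the NFP share is 14.1%, z = 0.031/0.0111 = 2.8, power 79%.
- Scenario 6: the NFP share is 0.14 + 0.82 × 0.0315 = 16.6%, z = 0.0057/0.0113 = 0.5, power 8%.

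**The case against.** **Other outcomes show the effect.** The three indicators keep all women and are reported first, so an even reduction would probably be seen at 24 months (79% power). This stands for effects that start early. It does not cover effects confined to later births.

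**The worst scenarios are not what the documents expect.** The 18% is stated only for the binary measure, and Protocol 4.2 ends participation when the child is two. A wrong sign needs a proportionally larger reduction after month 21 than before. If the effect fades instead (18% before month 21, 9% after), the planned difference is +0.5 months, with the right sign. This limits the claim: a wrong sign is possible but not the central expectation. Even under fading, planned power is 12%, against a restricted-mean difference of +1.8 months with 93% power.

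**The alternative is not uniformly better.** In scenario 5 the planned analysis has more than twice the power. True, and the plan should say so. That power still comes from a comparison that is not protected by randomisation when births are also averted.

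**The Addendum 1 precedent is weaker than it looks.** Its bounds are conditional on a significant difference in gestational age and are a robustness check; the main analysis there stays conditional. Fair. The precedent shows that the selection problem is recognised, not that the SAP has already settled on all-women analyses.

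**Part of the method is elsewhere.** Addendum 3 refers to the published trial protocol for its empirical approach, and the SAP says it will be updated for longitudinal outcomes. The finding therefore covers the protocol and SAP as they stand.

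**Undiluted effect.** With the 0.90 factor from Protocol 5.2, scenario 1 gives 0.9 × 2.39 = 2.15 months for the restricted mean. The planned difference is still zero.

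**Conclusion.** The concern holds. As written, the continuous interval is compared between groups selected by a post-randomisation event that NFP is meant to affect. The direction of the error is not fixed: the estimate can be zero, positive or negative depending on which births are averted. The zero under an even reduction needs no assumption about the 60-month share. The other sizes rest on the assumed 40% to 60% share, the piecewise-constant hazard, and reading the 14% as the 21-month rate.

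The reach is limited to one non-primary outcome in a later manuscript. The primary outcome and the 15- and 24-month indicators are unaffected. The plan should be changed, because this is the only listed birth-spacing outcome that could show effects beyond 24 months.

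**What to change.** - Make the main analysis time to next live birth in all women in the section 3.1 sample, censored at 60 months or at the end of vital-records coverage if earlier. Report Kaplan-Meier curves by arm and the difference in restricted mean time to 60 months.
- State the time origin: the index birth, or the date of fetal death for women with one. Alternatively, limit this outcome to women with an index birth.
- Keep the conditional mean as descriptive, beside the share of each arm with another birth by 60 months.
- State two limits. The restricted mean combines averted and delayed births and is less sensitive to pure postponement within 60 months. Women lost to the records, for example "because women enrolled in the trial moved out of state", count as birth-free. The binary indicators already treat them so, but over a shorter period.

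The cost is SAP wording and standard survival code on the same vital records. In statistical terms the price is lower power if NFP only postpones births within 60 months (24% against 57%).

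Two clerical corrections belong in the same edit of 3.3. The indicators are worded there as no birth within the period, the reverse of Table 3.1, and should follow the table. November 7, 2020 plus 120 days is March 7, 2021, so the two March dates should read 2021 and 2023; the September and December 2023 dates already agree with that.
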